6.3 SECONDARY ENDPOINTS

For any time-to-event outcomes that follow, the analysis cutoff date will be defined as the date upon which a data freeze is performed for an analysis.

6.3.1 DURATION OF RESPONSE (DOR)

DOR is defined as the time from Day 28 response (CR or PR) until the first of the following events occurs: progression of acute GVHD, death, any next-line GVHD therapy, or escalation of prednisone-equivalent steroid dose to 2.5mg/kg/day or more. DOR will be evaluated in the set of patients that attain a response (CR or PR) on Day 28. Progression is defined as the worsening by one stage or more from nadir in any acute GVHD target organ without improvement in other organs in comparison with the prior response. In the DOR context, the prior response refers to Day 28 response (CR or PR); nadir in an organ refers to Day 28 stage of this organ. For a patient in CR at Day 28, nadir is stage 0 in all target organs.

DOR, in days, is calculated as (Date of acute GVHD progression, death, next-line acute GVHD therapy, escalation of prednisone-equivalent steroid dose to 2.5mg/kg/day or more, or last known to be alive) – (Date of Day 28 Response) +1.

Table 7: DOR Definition

Situation	Date of Event or Censoring	Outcome
Death, acute GVHD progression, next-line acute GVHD therapy initiation, or steroid dose escalation $\geq 2.5\text{mg/kg/day}$ before or on analysis cutoff date	Date of event	DOR event
Death, acute GVHD progression, next-line acute GVHD therapy initiation, or steroid dose escalation $\geq 2.5\text{mg/kg/day}$; all events happened after analysis cutoff date	Analysis cutoff date	Censored
No event occurred, last known date alive is before or on analysis cutoff date	Last known date alive	Censored
No event occurred; last known date alive is after analysis cutoff date	Analysis cutoff date	Censored

DOR = Date of Event or Censoring – Date of Day 28 Response + 1

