3.2 Secondary Endpoints

3.2.1 Duration of Response (DOR)

The duration of response (DOR) is defined as time from the Day 28 response (CR or PR) to any of the following events: recurrence/progression of acute GVHD, new systemic salvage therapy for

acute GVHD, re-escalation of steroids to greater or equal to 2.5 mg/kg prednisone or equivalent, or death from any cause. Patients without any of these events will be censored at last follow up. DOR will be evaluated at 6- and 12-months post-randomization.

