5.7 Analysis of Secondary Endpoints

5.7.1 Duration of Response

Duration of response will be evaluated at 6- and 12-months post-randomization in the cohort of patients who achieve a Day 28 response. There will be a primary and secondary analyses of DOR. In the primary analysis, DOR is defined as the time from Day 28 response to progression, new salvage therapy for acute GVHD, death from any cause, or re-escalation of steroids to ≥ 2.5 mg/kg prednisone or equivalent. Patients without any of these events will censored at last follow up. For the secondary analysis, DOR will be defined as time from Day 28 response to death from any cause or new salvage therapy. Otherwise, patients are censored. For each definition, the probabilities of DOR will be estimated using the Kaplan-Meier method and compared between treatment arms using the log-rank test.

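### Duration of response fixes each organ's reference at its Day 28 stage, so a partial responder who clears later and then recurs to no more than that stage has no progression event

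*SAP*

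**What the plan says.** SAP 6.3.1 gives the rule for the GVHD component of DOR: "Progression is defined as the worsening by one stage or more from nadir in any acute GVHD target organ without improvement in other organs". It then fixes the reference: "nadir in an organ refers to Day 28 stage of this organ". For complete responders it adds: "For a patient in CR at Day 28, nadir is stage 0 in all target organs". Besides death, the other DOR events are "any next-line GVHD therapy, or escalation of prednisone-equivalent steroid dose to 2.5mg/kg/day or more".

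Nothing in SAP Table 7, 7.5.1, Table 18 or 7.9 lowers the reference if an organ improves after Day 28.

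The protocol words the event in two ways. Section 3.2.1 defines DOR as the "time from the Day 28 response (CR or PR) to any of the following events: recurrence/progression of acute GVHD", followed by the other components. Section 5.7.1, on the analysis, says "DOR is defined as the time from Day 28 response to progression, new salvage therapy for acute GVHD, death from any cause" and then adds steroid re-escalation; it does not mention recurrence. Neither section gives a reference stage. SAP 7.11 states that the only change from the protocol-specified analysis is the significance level for exploratory endpoints.

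DOR under this definition is step 2 of the hierarchy in SAP 7.1. A non-significant result there ends confirmatory testing of the later steps, which include non-relapse mortality and overall survival.

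**The concern.** A nadir is normally the lowest stage reached so far. Fixed at Day 28, it makes the scoring of a recurrence depend on when the organ cleared. An organ that reached stage 0 by Day 28 and later returns to stage 2 has progressed. An organ that was at stage 2 on Day 28, cleared two weeks later and then returned to stage 2 has not. Both patients have disease reappearing in an organ that had been clear, which Protocol 3.2.1 covers with the word recurrence.

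The other DOR components catch some of these cases but not all. Protocol 2.5.3.4 allows a flare to be treated with a steroid increase to below 2.5 mg/kg/day without scoring a failure, and Protocol 2.5.3.2 does not treat topical therapy as secondary systemic therapy. A recurrence managed in either way leaves no DOR event in the partial responder. By contrast, SAP 7.9 counts a missing acute GVHD assessment as a DOR failure.

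At stake is whether the second confirmatory endpoint measures the event that the protocol names, and whether the uncounted recurrences balance between arms.

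**Working it through.** **1. The rule applied to single-organ paths.** Stages are for lower GI at Day 28, at a later visit, and at a visit after that. Each path involves one organ, so the clause about improvement in other organs plays no part. The last two columns are the two possible repairs.

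| Day 28 status | Path | SAP 6.3.1 | Reappearance after stage 0 | Lowest stage since Day 28 |
|---|---|---|---|---|
| CR | 0, 0, 1 | event | event | event |
| CR | 0, 0, 2 | event | event | event |
| PR | 1, 0, 1 | none | event | event |
| PR | 2, 0, 2 | none | event | event |
| PR | 2, 0, 3 | event | event | event |
| PR | 2, 1, 2 | none | none | event |

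The asymmetry lies between rows 1 and 3 and between rows 2 and 4. It concerns the progression component only.

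**2. Expected responders.** The documents give no event count or power for DOR, so the primary design is used only to fix the denominators. Inputs from Protocol 5.2: 68 per arm, 50% vs 75%, one-sided 2.5%.

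- z = [0.25 × √68 − 1.96 × √(2 × 0.625 × 0.375)] / √(0.25 + 0.1875) = (2.062 − 1.342) / 0.661 = 1.088
- Power = 86.2%, against the stated 86%.
- Responders: 0.50 × 68 = 34 (placebo) and 0.75 × 68 = 51 (AAT).

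**3. Illustrative number of uncounted recurrences.** These are assumptions, not figures from the documents: 30–50% of responders are PR at Day 28; 40–70% of those clear later; 15–35% of the cleared recur to no more than their Day 28 stage with no other DOR event.

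- Low: 0.30 × 0.40 × 0.15 = 1.8%, or 0.6 of 34 and 0.9 of 51.
- High: 0.50 × 0.70 × 0.35 = 12.25%, or 4.2 of 34 and 6.2 of 51.

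**4. Illustrative difference between arms.** Further assumptions: flare rate f = 30% in both arms; a share c = 50% of PR clear later; 70% of flares in those patients do not exceed the Day 28 stage; CR share of responders is 60% (AAT) and 40% (placebo); no uncounted flare triggers another component. Counted flares = CR × f + (1 − CR) × [c × f × 0.3 + (1 − c) × f].

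- The bracket is 0.5 × 0.30 × 0.3 + 0.5 × 0.30 = 0.195.
- AAT: 0.6 × 0.30 + 0.4 × 0.195 = 25.8%.
- Placebo: 0.4 × 0.30 + 0.6 × 0.195 = 23.7%.
- Difference: 2.1 points where both rates were set to 30%. In general it is (0.6 − 0.4) × 0.7 × c × f = 0.14cf. This runs from 0.8 points (c = 0.3, f = 0.2) to 3.9 points (c = 0.7, f = 0.4).
- Standard error with 51 and 34 responders: √(0.258 × 0.742/51 + 0.237 × 0.763/34) = 9.5 points. So 2.1 points is 0.22 SE and 3.9 points is 0.41 SE.
- Exchange the two CR shares and the 2.1 points change sign. With equal CR shares and equal later clearing the difference is zero.

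**The case against.** The strongest defence is that a fixed reference fits the question asked. SAP 7.5.1 describes a durable response as keeping the CR or PR, and SAP 6.3.1 ties the prior response to Day 28. A patient at stage 4 before enrollment, 2 on Day 28, then 0, then 2 is still in PR against baseline and no worse than when the clock started. A complete responder who reaches stage 2 has lost the CR. This is a coherent reading, and it makes a full running nadir debatable: a path of 2, 1, 2 would become an event although the patient has only returned to the Day 28 response. It answers less well the case of an organ that cleared and then became active again, because Protocol 3.2.1 names recurrence.

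Three stronger readings are tempting, and the documents do not support them.

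- A reader might infer that such a patient has no DOR event at all. Next-line therapy, steroids of 2.5 mg/kg/day or more, and death still count.
- A reader might infer a plain undeclared departure from the protocol. Protocol 5.7.1 lists progression only and the protocol sets no reference stage for DOR, so the SAP partly fills a gap. The protocol's two sections differ between themselves.
- A reader might infer a bias against AAT. Protocol 5.2 assumes only that the combined CR/PR rate rises from 50% to 75%. It says nothing about the CR share among responders. If AAT turns non-responders into partial responders, the effect could favor AAT.

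It can also be said that step 3 of the hierarchy is unaffected. That is true, but step 3 drops progression entirely, so it does not recover these recurrences, and it is tested only if step 2 succeeds.

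**Conclusion.** The concern holds as a gap in the definition. Under SAP 6.3.1, recurrence in an organ that cleared after Day 28, up to its Day 28 stage, is not a progression event in a partial responder, while the same recurrence is an event in a Day 28 complete responder. This follows from the text and needs no assumption. It omits part of what Protocol 3.2.1 lists as a DOR event, although Protocol 5.7.1 is narrower, and SAP 7.11 is silent.

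The effect on the comparison between arms cannot be computed from the documents. It depends on the CR/PR mix and on later clearing in each arm. On the assumptions shown it is a fraction of a standard error with no established direction, and it shrinks further if some of these recurrences lead to next-line therapy: if half did, 2.1 points would become about 1. The primary endpoint is not touched. The point deserves correction because DOR is a confirmatory gate and the repair is cheap, not because a large bias has been shown.

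**What to change.** Reconcile SAP 6.3.1 with Protocol 3.2.1 and 5.7.1 by one of two routes.

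1. Count as a DOR event any reappearance (stage 1 or more) in an organ that reached stage 0 at or after Day 28. This is the narrower change. It follows the protocol's word recurrence and leaves a path of 2, 1, 2 without an event.
2. Define nadir as the lowest stage recorded from the Day 28 assessment up to the current one.

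Under either route, report the version with the fixed Day 28 reference as a sensitivity analysis and record the choice and its reason in SAP 7.11. Decide before any unblinded analysis of DOR. SAP section 1 allows revisions before the database hard lock, but the 6-month report in SAP 7.7.2 already describes outcomes, so the decision should come before that report.

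The cost is one sentence, one derivation and one extra analysis. No new data are needed: acute GVHD is staged weekly to Day 56 and at 3, 6 and 12 months. The downside is somewhat more events in partial responders. Some will rest on staging done away from the transplant center, because Protocol 4.3.2 requires direct observation there only on Days 28 and 56. Visits are also sparse after Day 86, so some clearing and recurrence will go unseen.

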6.3.2 NON-RELAPSE MORTALITY (NRM)

NRM is defined as death without prior relapse/progression for the primary disease. Relapse/progression is treated as a competing risk for NRM and defined in section 6.3.4. The NRM time is defined as the time from the date of randomization until the documented date of relapse/progression or death from any cause, whichever happens first. The outcome type is defined as shown in Table 8. All relapses/progressions and deaths occurring on or after the randomization date will be included. Patients who are event-free at the time of analysis will be censored at the last day known to be alive or at the analysis data freeze date, whichever is earlier. Patients experiencing event(s) after the analysis cut-off date will be censored at the analysis cut-off date.

Table 8: NRM and Relapse/progression Competing Risks Definition

Situation	Date of Event or Censoring	Outcome
Relapse/progression occurred before or on analysis cutoff date	Date of relapse/progression	Relapse/progression
Death without prior relapse/progression occurred before or on analysis cutoff date	Date of death	NRM
Death and/or relapse/progression occurred, all events happened after analysis cutoff date	Analysis cutoff date	Censored
No death or relapse/progression occurred, last known date alive is before or on cutoff date	Last known date alive	Censored
No death or relapse/progression occurred; last known date alive is after the cutoff date	Analysis cutoff date	Censored

Time of NRM = Date of Event or Censoring – Date of Randomization + 1

6.3.3 OVERALL SURVIVAL (OS)

OS is defined as the absence of death; failures for OS include deaths from any causes. The OS time is defined as the time from the date of randomization until the documented date of death from any cause. All deaths occurring on or after the randomization date will be included. Patients who are still alive at the time of analysis will be censored at the last day known to be alive or at the analysis data freeze date, whichever is earlier. Patients who died after the analysis cut-off date will be censored at the analysis cut-off date.

Time of OS, in days, is calculated as (Date of death or last known to be alive) – (Date of Randomization) +1.

Table 9: OS Definition

Situation	Date of Event or Censoring	Outcome
Death before or on analysis cutoff date	Date of death	Death
Death after analysis cutoff date	Analysis cutoff date	Censored
Last known date alive is before or on cutoff date	Last known date alive	Censored
Last known date alive is after the cutoff date	Analysis cutoff date	Censored

Time of OS = Date of Event or Censoring – Date of Randomization + 1

6.3.4 PROGRESSION FREE SURVIVAL (PFS)

PFS is defined as being alive and free of relapse/progression of the primary disease. Failures for PFS include death from any cause and disease relapse/progression. The PFS time is defined as the time from the date of randomization until the documented date of disease relapse/progression or death from any cause, whichever happens first.

Malignancy Relapse/progression Definition:

A subject's underlying disease (i.e., malignancy) relapse/progression information is collected in the case report form. Relapse is defined by either morphological or cytogenetic evidence of acute leukemia or myelodysplastic syndrome (MDS), consistent with pre-

transplant features, or radiologic evidence of lymphoma, documented or not by biopsy. Progression of disease applies to patients with lymphoproliferative diseases (lymphoma or chronic lymphocytic leukemia) not in remission prior to transplantation. The event is defined as an increase in the size of prior sites of disease or evidence of new sites of disease, documented or not by biopsy. In addition, the institution of any therapy to treat persistent, progressive, or relapsed malignancy, including the withdrawal of immunosuppressive therapy or donor lymphocyte infusion, will be considered evidence of relapse/progression regardless of whether the criteria described above were met.

- **Acute Leukemia:** Relapse will be diagnosed when there is:
 - Reappearance of leukemia blast cells in the peripheral blood; or
 - > 5% blasts in the bone marrow not attributable to another cause (e.g. bone marrow regeneration)
 - The development of extramedullary leukemia or leukemic cells in the cerebral spinal fluid
- **MDS:** Relapse will be diagnosed when there is:
 - Satisfaction of criteria for evolution into acute myeloid leukemia (blasts greater than 20%), or
 - Reappearance of pre-transplant morphological abnormalities detected in bone marrow specimens combined with a decrease in PB chimerism, OR
 - Reappearance of pre-transplant cytogenetic abnormality in at least one metaphase by routine metaphase cytogenetics or a positive test by FISH on each of two separate consecutive examinations at least one month apart, regardless of the number of metaphases analyzed
 - For patients with:
 - Less than 5% blasts: greater or equal to 50% increase in blasts to greater or equal to 5% blasts confirmed by flow cytometry
 - 5%-10% blasts: greater or equal to 50% increase to greater or equal to 10% blasts confirmed by flow cytometry

Lymphoproliferative Diseases: Relapse or progression will be diagnosed when there is:

- The appearance of any new lesion more than 1.5 cm in any axis during or at the end of therapy, even if other lesions are decreasing in size. Increased fluorodeoxyglucose (FDG) uptake in a previously unaffected site will only be considered relapsed or progressive disease after confirmation with other modalities. In patients with no prior history of pulmonary lymphoma, new lung nodules identified by CT are mostly benign. Thus, a therapeutic decision should not be made solely based on the positron emission tomography (PET) without histologic confirmation.

- At least a 50% increase from the nadir in the sum of the product diameters of any previously involved nodes, or in a single involved node, or the size of other lesions (e.g., splenic or hepatic nodules). To be considered a progressive disease, a lymph node with a diameter of the short axis of less than 1.0 cm must increase by $\geq 50\%$ and to a size of 1.5 x 1.5 cm or more than 1.5 cm in the long axis.
- Lesions should be PET positive if observed in a typical FDG-avid lymphoma or the lesion was PET positive before therapy unless the lesion is too small to be detected with current PET systems (<1.5 cm in its long axis by CT).
- In addition to the criteria above, patients with chronic lymphocytic leukemia (CLL) who present in complete remission prior to transplantation may fulfill the relapse definition if there is a reappearance of circulating malignant cells that are phenotypically characteristic of CLL.
- **Other Malignant Diseases:** Probable or definitive evidence of progression must be documented by biopsy, imaging, or peripheral blood findings that are diagnostic or otherwise consistent with that disease state.

Non-malignant Diseases: Patients with non-malignant diseases will be considered to have a transplant status of persistent/active disease. Graft failures will be considered a relapse of the disease.

All relapses/progressions and deaths occurring on or after the randomization date will be included. Patients who are still alive and free of relapse/progression at the time of analysis will be censored at the last day known to be alive and progression-free or at the analysis data freeze date, whichever is earlier. Patients experiencing relapse/progression or death after the analysis cut-off date will be censored at the analysis cut-off date.

Time of PFS, in days, is calculated as (Date of relapse/progression, death, or last known to be alive) – (Date of Randomization) +1.

Table 10: PFS Definition

Situation	Date of Event or Censoring	Outcome
Death or relapse/progression occurred before or on analysis cutoff date	Date of relapse/progression or death	PFS event
Death and/or relapse/progression occurred, all events happened after analysis cutoff date	Analysis cutoff date	Censored
No death or relapse/progression occurred, last known date alive is before or on analysis cutoff date	Last known date alive	Censored
No death or relapse/progression occurred; last known date alive is after analysis cutoff date	Analysis cutoff date	Censored

Time of PFS = Date of Event or Censoring – Date of Randomization + 1

6.3.5 GVHD-FREE SURVIVAL

GVHD-free survival is defined as being alive, free of active acute and chronic GVHD, free of any next-line GVHD therapy, and free of escalation of prednisone-equivalent steroid dose to 2.5mg/kg/day or more. The following exception is permitted for steroid escalation: if a patient received a prednisone-equivalent dose of 2.5mg/kg/day or more on the randomization day, maintaining this starting dose is not automatically considered a failure, but escalation to a dose higher than the starting one is a failure; moreover, if their dose is tapered below 2.5 mg/kg/day and later re-escalated to 2.5 mg/kg/day or above, they will be classified as a failure. Acute GVHD is defined per the MAGIC criteria (Harris et al. 2016) with grade 0 referring to no acute GVHD. Chronic GVHD is defined per the 2014 NIH Consensus Criteria. The proportion of patients with GVHD-free survival will be evaluated at Day 56 post-randomization. For the analysis of GVHD-free survival, a patient with a missing acute or chronic GVHD assessment will be considered to be a failure at the corresponding GVHD assessment Day. An acute or chronic GVHD assessment conducted out of window (refer to Section 7.1 for visit window definition) will be considered as missing.

6.3.6 ACUTE GVHD RESPONSE TO AAT/PTM

This endpoint focuses specifically upon the effect of the randomized treatment (AAT or PTM) alone on acute GVHD response, following a similar approach as for the primary endpoint at Day 28. The proportions of patients with CR, PR (including the subset with VGPR), and treatment failure (TF) will be described at Days 7, 14, 21, 28, 56, and 86 post-randomizations. The designation of TF consists of patients with NR, MR, and acute GVHD progression. The Day 86 response will be summarized only in patients remaining on study maintenance treatment (AAT/PTM) after Day 28. Patients who die, initiate either approved or unapproved next-line GVHD therapy, or have escalation of prednisone-equivalent steroid dose to 2.5mg/kg/day or more prior to an acute GVHD assessment will be classified as non-responders (NR) at the corresponding Day with the following exception: if a patient received a prednisone-equivalent dose of 2.5mg/kg/day or more on the randomization day, maintaining this starting dose is not automatically considered an NR, but escalation to a dose higher than the starting one is an NR; moreover, if their dose is tapered below 2.5 mg/kg/day and later re-escalated to 2.5 mg/kg/day or above, they will be classified as an NR. Patients with a missing acute GVHD assessment will be classified as non-responders (NR) at the corresponding Day. An acute GVHD assessment conducted out of window (refer to Section 7.1 for visit window definition) will be considered as missing.

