2.5.1.10 Study Drug Discontinuation Criteria

Patients that progress or are non-responders and receive ruxolitinib as next-line therapy are encouraged to continue study drug (AAT/PTM).

Study drug shall be discontinued and not re-instituted if any one of the following criteria is met:

- Patient does not receive study medication for 3 consecutive doses or 4 doses in total for any reason, including toxicity.
- Patients that receive next-line therapy other than ruxolitinib not approved by the BMT CTN 1705 Protocol Chairs.
- Relapse or progression of underlying malignancy.
- Pregnancy or initiation of breastfeeding during the study; refer to Section 4.4.5.
- Withdrawal of consent from study and/or study drug

The reason for discontinuation of study drug must be documented by the study team. All randomized patients, including those that did not receive any study drug, discontinued study drug and/or failed treatment, are evaluable for all endpoints of the study and should continue with protocol-specific follow-up and data collection unless the patient has specifically withdrawn consent to provide data.

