3.2.5 Proportion of Response

The proportion of patients with CR, PR (including subset with VGPR), and treatment failure (TF) will be described at Days 7, 14, 21, 28, 56 and 86 post-randomization. The Day 86 response will be assessed in patients remaining on maintenance treatment after Day 28. The designation of TF will consist of patients with NR, MR, progression or initiation of additional systemic (next-line) GVHD therapies (or escalation of steroids to ≥ 2.5 mg/kg/day of prednisone [or methylprednisolone equivalent of 2 mg/kg/day]). Death from any cause will also be considered a TF.

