2. Complete acute GVHD staging and grading information including assessments of rash, diarrhea, nausea/vomiting, weight and liver function tests weekly until Day 56, and 3, 6, and 12 months. Days 28 and 56 scoring must be performed by direct observation at the Transplant Center. Evaluations at other time points may be performed by clinicians familiar with assessing GVHD other than at the Transplant Center but the Transplant Center is responsible for collecting all required data. All GVHD treatment decisions must be made by the physician at the Transplant Center.
3. Liver function tests (bilirubin, alkaline phosphatase, AST, ALT) weekly until Day 56, and at 3 months, 6 months, and 12 months.
4. Chronic GVHD assessment at Days 28 and 56, and months 3, 6 and 12.
5. GVHD prophylaxis medication (if available) weekly through Day 28.
6. CBC with differential, platelet count on Days 14, 28, 56, and 86.
7. Toxicities at Day 120, 6 months and end of treatment (EOT).
8. Infections up to 3 months are reported on the event driven infection forms. Per protocol section 4.4.1 infections are anticipated events and do not require reporting as an AE/SAE.
9. Corticosteroid dose (including administered dose and patient weight) weekly until Day 56, and at months 3, 6 and 12 and/or EOT.

10. Second-line immune suppressive therapy weekly until Day 56 and at months 3, 6 and 12 and/or EOT.
11. Patient-reported outcome measures at Day 28, Day 56, and 6 months. Only English- and Spanish-speaking patients may participate in the MDASI HQL component of this trial; only English-speaking patients may participate in the PROMIS HQL component of the trial. Adolescent versions should be completed by patients who are less than 18 years of age at the time of enrollment Surveys may not be completed by surrogates.*
12. Blood research samples for serum AAT levels in peripheral blood in peripheral blood at Days 0, 8, 16, 24, 28, and 56. Samples should be drawn just prior to each study drug infusion (and within 15-45 minutes post-end of infusion for the Day 16, 28, and 56 samples). See APPENDIX B for further details.*

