4.2 STATISTICAL DESIGN AND SAMPLE SIZE DETERMINATION

The primary hypothesis is that the odds ratio for the overall response (CR+PR) at Day 28 between the treatment groups, adjusted for treatment center and GVHD risk (MN high vs. standard risk), is greater than 1 (AAT+CS versus PTM+CS). The primary analysis will be based on a Wald test from a logistic mixed model with the overall response as the outcomes, testing the odds ratio of treatment assignment, as described in section 6.4.1.1. The required sample size for this study is approximated using a two-sample Z-test of the difference in response rates. Historical control data indicate that the overall response rate at Day 28 for high risk acute GVHD is approximately 50%. We anticipate that AAT+CS treatment will increase the Day 28 overall response rate to 75%, corresponding to a 25% effect size. To perform a one-sided test of the superiority of AAT+CS over PTM+CS with one interim analysis for futility, we use a two-stage design with one interim analysis for futility based on a Gamma family error spending function with $\gamma = -8$. The interim futility analysis was chosen to occur after 76 patients are evaluable for Day 28 response, at a 56% information fraction. This design specification and the two-sample Z-test sample size calculation imply that a sample size of 136 patients (68 per arm) is required to sufficiently maintain a one-sided type I error of 2.5% while providing 86% statistical power for a one-sided test to detect a 25% effect size.

Operating characteristics of this sequential design with a two-sample Z-test of response rates are shown in Table 4 as an approximation to the operating characteristics provided by a logistic mixed model in this setting. Kahan and Morris 2012 demonstrated that a stratified analysis improves statistical power for a specific set of analysis techniques. Based on their findings, we expect that the power provided by an unadjusted analysis via a two-sample Z-test comparing proportions is a lower bound to the power provided by the specified logistic mixed model.

Table 4: Group Sequential Design Stopping Thresholds for Z-test of Proportions with One-Sided Type I Error 2.5%, Power 86% and an Effect Size of 25%

Info. Fraction	Sample Size	Nominal Cumulative Type II Error Rate	Futility Boundary Scales			Probability of Stopping Early for Futility	
			Difference in Proportions	Z-Statistic	Conditional Power at Alternative	Under Null	Under Alternative

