7.5.6 ACUTE GVHD RESPONSE TO AAT/PTM

The proportions of patients with CR, PR, and TF will be tabulated by treatment arm at Days 7, 14, 21, 28, and 56 for all patients in the ITT population and at Day 86 for the subset of patients that remained on study maintenance treatment after Day 28. Goodman simultaneous 95% CIs (Goodman 1965) will be provided for the response category proportions. These proportions will be compared between treatment arms using Fisher's exact test. If a patient does not complete the acute GVHD assessment on an evaluation day for any reason (e.g. missed visit, withdrawal from the study, loss to follow-up), they will be assigned as a TF on that Day. Moreover, patients who die, initiate either approved or unapproved next-line GVHD therapy, or have escalation of prednisone-equivalent steroid dose to 2.5mg/kg/day or more prior to an acute GVHD assessment will be classified as non-responders (NR) at the corresponding Day.

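### The Day 86 response comparison drops most Day 28 failures from the denominator, so it does not compare randomised groups and can dilute or hide a benefit

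*SAP*

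**What the plan says.** Two secondary endpoints report CR, PR and treatment failure (TF) at Days 7, 14, 21, 28, 56 and 86: response to AAT/PTM (SAP 6.3.6, 7.5.6) and response allowing for approved next-line therapy (SAP 6.3.7, 7.5.7). Through Day 56 the denominator is the whole ITT population. For the last visit SAP 6.3.6 states: "The Day 86 response will be summarized only in patients remaining on study maintenance treatment (AAT/PTM) after Day 28". SAP 7.5.6 and 7.5.7 both tabulate the results "at Day 86 for the subset of patients that remained on study maintenance treatment after Day 28" and compare arms by Fisher's exact test. Protocol 3.2.5 has the restriction too: "The Day 86 response will be assessed in patients remaining on maintenance treatment after Day 28".

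Under Protocol 2.5.1.7 and SAP 3.5, study drug continues after Day 28 only in patients in CR or PR at Day 28. Those who reach CR or PR on study drug plus ruxolitinib, or plus another approved next-line therapy, may also continue.

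Other text points to all patients:
- Protocol 2.5.1.10: "All randomized patients, including those that did not receive any study drug, discontinued study drug and/or failed treatment, are evaluable for all endpoints".
- Protocol 4.3.2 schedules acute GVHD staging "weekly until Day 56, and 3, 6, and 12 months", with no condition on treatment status. Protocol Table 4-1 and SAP Table 1 agree and place the 3-month visit at Day 86.
- Protocol 5.7.5 lists Day 86 with the other days and does not restrict it.
- SAP 6.3.7 says that it uses the same ITT population as 6.3.6.

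**The concern.** The Day 86 subset is defined by something that happens after randomisation and that the treatment is intended to change. If AAT raises the Day 28 response rate, more AAT than placebo patients enter the Day 86 denominator, and the extra ones are patients who would have failed on placebo. The comparison then asks how well response holds among those selected as responders. It no longer asks which randomised arm has more patients in response.

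The Day 86 figures would stand beside rows for Days 7 to 56 that do compare randomised groups. A reader who follows the rows across could conclude that a benefit seen at Days 28 and 56 had faded, when only the denominator had changed.

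**Working it through.** **Inputs from the documents.** 68 patients per arm (SAP 3.5). Day 28 response of about 50% on PTM, and the expectation that "AAT+CS treatment will increase the Day 28 overall response rate to 75%, corresponding to a 25% effect size" (SAP 4.2). Secondary tests are two-sided at 5% (SAP 7.1).

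**Inputs assumed, because the documents do not give them.** The share of Day 28 responders still in response at Day 86 (central value about 80% in each arm, range 50% to 90%). The share of Day 28 failures who stay on maintenance through the next-line route (0% to 30%).

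**Step 1: the plan's own figure.** SAP 4.2 says that 136 patients "sufficiently maintain a one-sided type I error of 2.5% while providing 86% statistical power". With the pooled variance under the null and the unpooled variance under the alternative:

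z = [0.25 × √68 − 1.96 × √(2 × 0.625 × 0.375)] / √(0.50 × 0.50 + 0.75 × 0.25) = (2.062 − 1.342) / 0.661 = 1.09, so power = 86.2%.

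The stated 86% is reproduced, so these rates and sizes are the plan's. The plan states no power for Day 86.

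**Step 2: who leaves.** Day 28 responders are 0.50 × 68 = 34 (PTM) and 0.75 × 68 = 51 (AAT). Day 28 failures are 34 and 17. Without the next-line route, 50% of the PTM arm and 25% of the AAT arm drop out of the Day 86 denominator, all of them failures.

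**Step 3: the 6.3.6 endpoint at about 80% durability.** Still in response at Day 86: 0.80 × 34 = 27.2, taken as 27, and 0.80 × 51 = 40.8, taken as 41. Day 28 failures are counted as failures at Day 86. If 20% of failures stay on maintenance, 0.20 × 34 = 6.8 (7) and 0.20 × 17 = 3.4 (3) patients are added to the denominators as TF.

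| Denominator | PTM | AAT | Difference | Fisher p |
|---|---|---|---|---|
| ITT | 27/68 (40%) | 41/68 (60%) | about 21 points | 0.025 |
| Subset, no failure stays | 27/34 (79%) | 41/51 (80%) | about 1 point | 1.0 |
| Subset, about 20% of failures stay | 27/41 (66%) | 41/54 (76%) | about 10 points | 0.36 |

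**Step 4: sensitivity to durability, equal in both arms, no failure staying.** The ITT difference is 0.75s − 0.50s = 0.25s, where s is the durability. The subset difference is s − s = 0.

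| s | ITT rates | ITT difference | Fisher power, ITT | Fisher power, subset |
|---|---|---|---|---|
| 50% | 25.0% vs 37.5% | 12.5 points | 29% | 5% |
| 70% | 35.0% vs 52.5% | 17.5 points | 47% | 4% |
| 90% | 45.0% vs 67.5% | 22.5 points | 70% | 3% |

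**Step 5: sensitivity to the next-line route, s = 70%.** If 10% to 30% of Day 28 failures in each arm stay on maintenance and count as TF, the subset difference is about 4 to 10 points, against 17.5 points in ITT.

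**Step 6: the 6.3.7 endpoint.** Approved next-line therapy is not a failure here, so Day 28 failures may be in response at Day 86. If 30% of them were (assumed), 0.30 × 34 = 10.2 (10) and 0.30 × 17 = 5.1 (5) responders are added. ITT becomes 37/68 vs 46/68 (54% vs 68%, p = 0.16). The table in step 3 therefore does not carry over to this endpoint.

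**The case against.** **Nothing confirmatory depends on this test.** SAP 7.1 treats any test outside its seven-step hierarchy as descriptive, and Day 86 response is not in the hierarchy. The treatment effect is tested as the primary endpoint at Day 28. At Day 56 it is shown in ITT for response and for GVHD-free survival. This stands, and it limits the point to how one secondary result will be read.

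**The restriction is a permitted exception.** Protocol 5.5.3 and SAP 7.1 both allow departures from the default population where these are specified, and the Day 86 restriction is specified. A reader might infer from the ITT sentence in SAP 6.3.7 that the plan breaks its own population rule. The documents do not support that: the same section states the Day 86 restriction, and the sentence mainly contrasts how the two endpoints classify next-line therapy.

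**The subset may answer a different question.** Day 86 falls 30 days after the last scheduled maintenance dose, so the row could describe whether response holds once maintenance ends. The documents do not give this reason, but it is plausible. It supports keeping the subset as a description. It does not support a between-arm test in that subset.

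**Not every Day 28 failure leaves.** Patients in CR or PR on study drug plus ruxolitinib or another approved therapy stay in the denominator. A Day 28 non-responder without next-line therapy or steroid escalation could also respond later. This stands. The 79% vs 80% result is a limiting case.

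**A reversed sign is possible but unsupported.** A reader might infer that the subset will favour placebo. If 37 rather than 41 AAT responders held, ITT would be 40% vs 54% (p = 0.12) and the subset 79% vs 73% (p = 0.61). That requires durability assumed to be worse on AAT, which nothing in the documents suggests, and neither comparison is significant.

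**Conclusion.** The concern holds in limited form. At Day 86 only, both response endpoints compare groups selected largely by Day 28 response, and the comparison can dilute or hide a benefit. For 6.3.6, at the design rates and about 80% durability in each arm, an ITT difference of about 21 points shrinks to about 1 point if no Day 28 failure stays on maintenance, and to about 10 points if about 20% stay. Durability, the share staying, and Day 28 failures remaining failures are all assumptions. For 6.3.7 the direction of the concern is the same, but the gap would differ and is not estimated here.

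A reader might go further and infer that a real benefit will disappear, or that the trial's conclusion is at risk. The documents support neither reading. The size depends on quantities that they do not give, and the primary conclusion and the familywise error rate are unaffected. This is an inexpensive improvement to a descriptive secondary result.

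**What to change.** In SAP 6.3.6, 6.3.7, 7.5.6 and 7.5.7, analyse Day 86 in the ITT population, applying to each endpoint the failure rules that it already uses at Days 7 to 56. These cover death, steroid escalation, missing or out-of-window assessment, and next-line therapy (any for 6.3.6, unapproved only for 6.3.7). Keep the on-maintenance subset as a labelled descriptive table without a between-arm test, and define there what counts as having remained on maintenance.

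The cost is SAP wording, plus either alignment of Protocol 3.2.5 or an entry in SAP 7.11, which lists changes from the protocol-specified analysis. Reported Day 86 response rates will be lower in both arms. No new data are needed, because Day 86 staging is already scheduled for all patients.
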